6.2. Side effects of drug

Losartan is an FDA-approved angiotensin receptor blocker that is widely prescribed for treatment of hypertension, heart failure, and for renal protective effects in diabetics. The dose proposed in this study is well tolerated by non-hypertensive patients without significant effect on blood pressure. The most common side effects are fatigue and dizziness. Serious adverse events that are rare include angioedema, hypotension, renal dysfunction, blood dyscrasias, hepatitis or rhabdomyolysis. According to the FDA-approved prescribing information, the adverse event profile is as follows:

“Cozaar has been evaluated for safety in more than 3300 adult patients treated for essential hypertension and 4058 patients/subjects overall. Over 1200 patients were treated for over six months and more than 800 for over one year. In general, treatment with Cozaar was well tolerated. The overall incidence of adverse experiences reported with Cozaar was similar to placebo. In controlled clinical trials, discontinuation of therapy due to clinical adverse experiences was required in 2.3 percent of patients treated with Cozaar and 3.7 percent of patients given placebo.”³⁴

“In the RENAAL study involving 1513 [Type II Diabetic Patients with Nephropathy] patients treated with Cozaar or placebo, the overall incidences of reported adverse experiences were similar for the two groups. Cozaar was generally well tolerated as evidenced by a similar incidence of discontinuations due to side effects compared to placebo (19% for Cozaar, 24% for

placebo). The adverse experiences, regardless of drug relationship, reported with an incidence of $\geq 4\%$ of patients treated with Cozaar and occurring more commonly than placebo, on a background of conventional antihypertensive therapy are shown in the table below.”³⁵

	Losartan and Conventional Antihypertensive Therapy Incidence % (n=751)	Placebo and Conventional Antihypertensive Therapy Incidence % (n=762)
Body as a Whole		
Asthenia/Fatigue	14	10
Chest Pain	12	8
Fever	4	3
Infection	5	4
Influenza-like disease	10	9
Trauma	4	3
Cardiovascular		
Hypotension	7	3
Orthostatic hypotension	4	1
Digestive		
Diarrhea	15	10
Dyspepsia	4	3
Gastritis	5	4
Endocrine		
Diabetic neuropathy	4	3
Diabetic vascular disease	10	9
Eyes, Ears, Nose and Throat		
Cataract	7	5
Sinusitis	6	5
Hemic		
Anemia	14	11
Metabolic and Nutrition		
Hyperkalemia	7	3
Hypoglycemia	14	10
Weight gain	4	3
Musculoskeletal		
Back pain	12	10
Leg pain	5	4
Knee pain	5	4
Muscular weakness	7	4
Nervous System		
Hypesthesia	5	4
Respiratory		
Bronchitis	10	9
Cough	11	10
Skin		
Cellulitis	7	6
Urogenital		
Urinary tract infection	16	13

Figure 2: Adverse events in the RENAAL study

6.3. Handling of drug

Study drugs will be supplied by a central drug distribution center and shipped to the investigators from a central drug repository. The study drug will be kept in a secure, limited access, storage area within a controlled, appropriate temperature range (room temperature). Each container of study medication will be identified by protocol name and labeled as required by federal law. Study drug receipt, distribution, and destruction will be documented in the drug accountability log. Adherence will be monitored by capsule count at follow-up visits. Unused study drug distributed to participants enrolled in the study should be returned to the clinic site. Unused drug will be destroyed at the clinical sites in accordance with the local policy and procedures.

6.4. COPD treatment

All participants enrolled in this study will continue to have their usual care for COPD as determined by their primary care provider or their usual COPD caregiver. No treatments will be discontinued. Study physicians will render emergency care for participants, refer to appropriate treating sources, and confer with treating sources, but will not provide comprehensive medical care to participants. With permission of the participant, treating physicians will be notified of the participant's enrollment in the study and results of study evaluations, e.g., spirometry, as appropriate.

7. Specific procedures

7.1. HRCT scans

HRCT scans of the lung will be acquired from individuals with COPD at V1 to confirm emphysema, and if eligible and randomized, at V7 (total of two scans). These data will be obtained specifically for research purposes using standardized protocols for different model scanners. Variation between scanners is minimized by designating the same scanner to be used for all scans on an individual before and after study treatment. The participant should have taken 2 puffs of albuterol within 6 hours of the HRCT scan.

For the HRCT scans:

- A pregnancy test will be administered at each visit before imaging for women of child bearing potential
- The lungs and trachea will be included
- The scanning protocol will begin below the lung bases and end above the lung apexes at the mandible
- Scans will be performed with the subjects in the supine position
- Each participant will have one standard scout (AP/PA) scan over the chest at Total Lung Capacity (TLC). Then a complete chest HRCT will be done at Total Lung Capacity (TLC)

Since the scans will be done at TLC, it is important for the coordinators and radiology technologists to ensure that the participant is appropriately coached prior to performing the actual scanning procedures. Study coordinators will be provided with a script to coach participants in the appropriate breathing technique to take and hold a TLC breath during spirometry prior to the HRCT exam. They will also provide the script for the radiology technologist to coach participants in the breathing technique. The scan will take about one hour including preparation and coaching. In order to minimize errors in scan acquisition, we will ask coordinators to accompany the participants to the HRCT scanner and provide the radiology technologist with the LEEP HRCT protocol including the proper acquisition parameters to program into the HRCT scanner. The model and serial identification number of the scanner will be recorded so that the same scanner is used for the second scan.

7.2. Pulmonary Function Testing

Spirometry before and after 2 inhalations of albuterol will be performed in accordance with ATS/ERS recommendations and PTC procedures. Spirometry is a common clinical test used to diagnose asthma, COPD, and certain other conditions that affect breathing. It measures how much and how fast air is inhaled and exhaled. It should be administered at the same time of the day. Spirometry reference values will be those of Hankinson et al from NHANES³⁶.

7.3. Randomization

Treatment assignment will be randomly allocated in a 1:1 ratio with stratification by clinic using a permuted block randomization scheme. Randomization will occur at V2 after the participant meets all eligibility criteria. The clinic staff will complete a randomization form for each eligible participant and enter it into a web-based randomization system. Eligibility criteria are verified via computer program, which then provides a unique study treatment assignment number according to an encrypted table on the server; the assignment number will correspond to a specific drug bottle.

The initial drug supply will be dispensed and a tear-off label will be affixed to a study form to provide an audit trail for drug distribution.

7.4. Phlebotomy and biospecimens

Whole blood and serum will be collected for measurement of complete blood counts and serum chemistry panels. The purpose of this testing is to monitor for potential adverse events that might lead to discontinuation of study treatment.

For participants willing to provide specimens for future analyses, (e.g. possible biomarker analysis), additional blood and urine specimens will be collected and stored at the ALA ACRC biospecimen repository. Specimens will be stored at -70 or -80C at the local site and shipped periodically in batches on dry ice for storage at the biospecimen repository.

Approximately 10 mL of blood is collected by venipuncture at V1, V4 and V7. Two 5 mL tubes are transmitted to the local hospital laboratory without processing for measurement of CBC and chemistries. Also, approximately 20 mL of blood is collected at V2, V5, and V7. This will be divided into eight, 1mL aliquots of serum and plasma for freezing and bulk storage pending shipping. DNA will be collected at V2. Instructions for processing the blood are provided in the manual of operations. Note that the total blood drawn at V7 is approximately 30mL for lab testing and for storage.

Approximately 20 mL of urine is collected by clean catch and is divided into 1.8 mL aliquots for freezing and storage pending shipping to the biorepository.

7.5. Unmasking

Unmasking of treatment assignment before the end of participant's treatment period is rarely necessary. If adverse events occur that may be related to the study treatment, then the study treatment is stopped and the participant continues scheduled follow-up.

Routine unmasking will occur at the end of the participant's V7 visit. The treatment assignment will only be provided to the participant and not the staff at the clinical center. Sealed envelopes with treatment assignment are provided to the clinic to provide the participants. In addition,

clinics can contact the DCC if necessary for unmasking information. All participants are provided with a wallet card that provides information that they are participating in a clinical trial and gives the contact numbers of personnel at the clinic.

7.6. Treatment termination

Participants may be withdrawn from the treatment if they have a serious adverse event or are intolerant of the treatment. All participants will be asked to return for study visits in order to maintain the intent to treat paradigm for the primary analysis. Participants will be treated by their usual COPD care provider according to best medical judgment regardless of whether they continue to use study treatment. Any female participant with a positive pregnancy test at any time during the study will be taken off study drug and followed to the outcome of pregnancy.

8. Analysis plan

8.1. Primary analysis

The primary goal of analysis is to precisely estimate the difference in response between the losartan and placebo groups by comparing between-group means of changes from baseline pct950 over the time course of treatment. The secondary goals require estimation of analogous differences in response trajectories separately for each secondary response variable. For analytic methods, we propose a series of generalized linear mixed models (GLMMs) for responses (Y) with possibly g -transformed) expected primary or secondary responses, $g(E(Y_{ij}|b_{0i}, \beta_i X_{ij}))$, where 1.) $(\beta_0 + b_{0i})$ for the i^{th} patient response is a random intercept (to account for serial correlations in the within-patient responses) with fixed mean β_0 and random normal distributed offsets b_{0i} , with mean zero and standard deviation $\sigma_{b_{0i}}$ and 2.) X_{ij} are fixed values of j^{th} covariate for the i^{th} patient and β_i is the fixed unknown regression coefficient to be estimated for covariate X_j . Covariates will include site (14 binary spline indicator variables for the 15 category site stratification), baseline values of the Y response, an indicator variable for treatment group ($trt = 1$ losartan, 0 placebo), and either spline indicators for time or a continuous function for the fixed time trend in mean response, and, if needed, interaction terms between the time covariates and the (trt) treatment group indicator. The primary outcome is change in pct950 from baseline after 48 weeks of treatment ($Y = \text{pct950} - \text{pct950}_{b_i}$) and $g(\cdot)$ is the identity function, so the above model simplifies to $Y_i + \varepsilon_i = E(Y_i | b_{0i}, X_i) = \beta_0 + b_{0i} + \beta_1 trt + \beta_2 \text{pct950}_{b_i} + \{\beta_j X_{ij}\} + \varepsilon_{ij}$, where β_0 is the intercept for the fixed effects, b_{0i} is the normal $(0, \sigma_{b_{0i}})$ random intercept offset for each participant, β_1 is the primary losartan vs placebo treatment effect = mean difference in 48 week change in pct950 from baseline, losartan vs. placebo, $\{\beta_j\}$ is the set of regression coefficients to account for stratification by site, and ε_i is a normal $(0, \sigma^2)$ random error for the i^{th} change from baseline in pct950. The primary analysis will focus on β_1 , = mean losartan vs. placebo mean change over 48 weeks in pct950. We will estimate a 95% confidence interval for the losartan vs placebo mean difference, β_1 , using the regression estimate and the t -distribution; we will reject the null that losartan is equivalent to placebo if the 95% interval excludes 0.0. A robust variance estimate³⁷ will be used to guard against incorrect inferences due to misspecification of the assumed serial correlation structure among repeated observations on each subject.

The primary analysis will be intention-to-treat so that the indicator trt is the group to which the person is randomized without regard to whether they complied with the treatment assignment or not. We anticipate some degree of loss-to-follow-up (less than 10%) that will not affect our analyses. However, the regression model above will be estimated using the method of maximum likelihood so that missing data will effectively be imputed by their expected values given the other measurements. If the loss-to-follow is 10% or greater, then multiple imputation will be used to construct the 95% confidence limits for β_1 estimated across 50 imputations of the dataset.

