2.3. Trial design /Schema

The trial is a parallel, randomized, placebo-controlled trial with two treatment groups, losartan at 100 mg/day and placebo. Participants will be randomly assigned in equal allocation to one of two treatments. The treatment period is 48 weeks with follow-up visits at 12-week intervals. Participants assigned to losartan will start with a dose of 50 mg/day; participants assigned to placebo will start with one capsule per day. A titration visit will be done at 2 weeks; if the systolic BP is >90 mm Hg and the diastolic BP is >60 mm Hg, the drug dose will be increased to 100 mg per day or matching placebo will be increased to two capsules per day. Symptoms, lung function, and specimens are collected at baseline and select follow-up visits. HRCT will be done at baseline and 48 weeks.

[figure not shown]

Figure 1: LEEP Trial design - schema

PFT: Pulmonary Function Test; HRCT: High Resolution Computed Tomography

3. Eligibility criteria

Participants with mild to severe COPD will be screened using the criteria below. Participants will be asked to sign informed consent before any screening procedures are performed.

3.1. Inclusion criteria:

- Age of 40 years or older at V1, either gender
- Mild to severe COPD (post-BD FEV₁/FVC ratio \leq 0.70 and FEV₁ 20-80% predicted) at V1
- Current or former smoker (\geq 10 pack-year history at V1)
- HRCT Scan with 5-35% of voxels with density $<$ -950 Hounsfield Units (HU) at V1
- Ability to understand and willingness to sign consent documents

3.2. Exclusion criteria:

- Current therapy with angiotensin converting enzyme (ACE) inhibitor or angiotensin receptor blocker (ARB)
- Known intolerance to ACE inhibitor or ARB
- History of angioedema
- Conventional indication for ACE inhibitor or ARB (including history of myocardial infarction, known cardiomyopathy)
- Renal insufficiency (GFR $<$ 30 mL/min by Cockcroft-Gault calculation)
- Current regular use of NSAIDs defined as daily use 5 or more days of the week for more than one month
- Current treatment with a potassium sparing diuretic
- Potassium supplementation or serum potassium level of \geq 5.0 mEq/L at V1
- COPD exacerbation requiring treatment within 6 weeks at V1
- Chronic systemic corticosteroid use $>$ 10mg/day of prednisone
- Resting SpO₂ $<$ 89% on 2L nasal cannula continuous flow; unless at altitude $>$ 4,000 feet, then resting SpO₂ $<$ 89% on 4L NC continuous flow

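### The primary model carries a participant random intercept that one change score per person cannot identify, and separately leaves open the finite-sample form of the variance behind the deciding 95% interval

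*Combined protocol and SAP*

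**What the plan says.** Section 2.3 states that "HRCT will be done at baseline and 48 weeks". Section 7.1 agrees: one scan at screening and a second, "if eligible and randomized, at V7 (total of two scans"). The primary response in section 8.1 is therefore one number per person, the 48-week change in pct950.

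Section 8.1 sets up one mixed-model family for primary and secondary responses, then simplifies it for the primary outcome. The simplified equation keeps a "random intercept offset for each participant" beside a normal residual error. Its fixed part has an intercept, treatment, baseline pct950 and site, the last through "14 binary spline indicator variables for the 15 category site stratification".

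For inference, section 8.1 bases the interval on the regression estimate and a t-distribution, and gives the decision rule: "we will reject the null that losartan is equivalent to placebo if the 95% interval excludes 0.0". A robust variance is added to guard against "misspecification of the assumed serial correlation structure among repeated observations on each subject". On missing data it says that "the regression model above will be estimated using the method of maximum likelihood", and then: "If the loss-to-follow is 10% or greater, then multiple imputation will be used". Section 8.2 refers back to maximum likelihood and robust variance as the methods of the primary analysis. Section 8.5 sets alpha at 0.05, two-sided.

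No degrees of freedom are given for the t-distribution, REML is not mentioned, and no finite-sample form of the robust variance is stated. That variance is defined only by a reference to a textbook chapter.

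**The concern.** There are two distinct points, with different consequences.

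First, a repeated-measures specification has been carried over to an outcome that is not repeated. A random intercept and a residual error compete for the same single observation per person. The stated reason for the robust variance, serial correlation within a person, also does not arise for this outcome, although such a variance can still protect against unequal variances.

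Second, the interval for the treatment coefficient decides the trial, and its actual level depends on how the variance is computed. The maximum likelihood variance divides the residual sum of squares by n, and the basic sandwich uses raw residuals. With 17 fitted parameters, both are too small on average, and a t critical value does not compensate. The plan as written allows analyses at slightly different true levels.

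**Working it through.** **Inputs from the plan.** Two scans per person (2.3, 7.1); 14 site indicators plus intercept, treatment and baseline (8.1); two-sided alpha 0.05, delta 2, SD 4, power 90%, 88 per group raised to 110 (8.5); switch to multiple imputation at 10% loss (8.1).

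**The plan's own sample size.** 2 × 4² × (1.960 + 1.282)² / 2² = 84.06, so 85 per group by the normal formula and 86 by the t-test. The stated 88 is slightly conservative (power 91.3% by z, 91.0% by t). 88 / 0.8 = 110 per group, or 220 in total. Below the 10% switch, the largest loss is 21 of 220 (9.5%), which leaves 199. The range for the maximum likelihood branch is therefore n = 220 to 199.

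**Step 1: redundancy.** With one row per person, Var(Y) = (σ_b² + σ²)·I. The likelihood depends only on the sum, and the covariance of the fixed effects, (σ_b² + σ²)(X'X)⁻¹, does not depend on the split. As a check, the intercept's share of the total variance was set at 0, 10, 50, 90 and 99% in one simulated dataset per n. The log-likelihood was identical to 8 decimals, the treatment estimate matched least squares to 1e-14, and the maximum likelihood standard error was the same fraction of the least-squares one at every share (0.9606 at n = 220, 0.9563 at n = 199).

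**Step 2: parameter count.** 1 + 1 + 1 + 14 = 17.

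**Step 3: level with an uncorrected maximum likelihood variance.** The ratio of the uncorrected to the correct standard error is r = √((n − 17)/n). Type I error = 2·P(T > r·t₀.₉₇₅), with T on n − 17 df.

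| n | df | r | Interval too narrow by | t₀.₉₇₅ | Type I error |
|---|---|---|---|---|---|
| 220 | 203 | 0.9606 | 3.9% | 1.9717 | 5.96% |
| 199 | 182 | 0.9563 | 4.4% | 1.9731 | 6.08% |

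The last column is also the largest correctly computed p-value that would be declared significant: about 0.060 and 0.061.

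**Step 4: what drives the excess.** At n = 220 with the uncorrected variance, the level is 6.12% with z, 5.98% with t on n − 1 df and 5.96% with t on n − 17 df. With the corrected variance it is 5.14% with z and 5.00% with t on n − 17 df. The df choice moves the level by about 0.15 points; the variance form moves it by about 1 point.

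**Step 5: the basic sandwich.** The closed form above is for the maximum likelihood variance, so the sandwich was simulated: 1,000,000 trials per n, Monte Carlo SE 0.02 points, every variance referred to t on n − 17 df. Assumptions not in the plan: 15 uneven sites, permuted blocks of 4, and baseline pct950 uniform over 5 to 35 (the eligibility range).

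| Variance | n = 220 | n = 199 |
|---|---|---|
| Maximum likelihood, uncorrected | 5.98% | 6.11% |
| Basic sandwich (HC0) | 5.98% | 6.11% |

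Least squares, HC1 and HC2 gave 5.02% to 5.04% across both sizes. With unequal variances (arm SDs in ratio 3:5, or SD proportional to baseline), the uncorrected forms gave 5.94% to 6.12% and the corrected forms 4.96% to 5.05%.

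**The case against.** The strongest reply is that the plan is silent and does not say that the variance is uncorrected. Its cited chapter may specify a correction, the software may apply one, and naming a t-distribution suggests that finite samples were in mind. This stands. A reader might infer that the trial's test runs at 6%. The documents do not support that; they show only that the estimators they name, used in basic form, would give it.

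A reader might also infer that the random intercept biases the result or causes the inflation, or that the missing degrees of freedom do. Neither follows. The intercept contributes nothing to the 6% (Step 1) and the degrees of freedom contribute little (Step 4). The intercept is best seen as a drafting carry-over from a shared model family that does suit outcomes with repeated post-baseline values.

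It is fair, too, that section 8.1 brings in maximum likelihood mainly for missing data and assigns the standard error to the robust variance. The plan-relevant case is then the basic sandwich, whose figures rest on simulation under assumed site sizes, blocks and baseline distribution. They agree with the closed form, so this alters the emphasis and not the size.

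Last, one percentage point is small. That is conceded. But this is the only primary test, and the choice should not remain open once data are seen.

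**Conclusion.** The point holds as a specification gap in the primary inference, with a modest and conditional consequence. The random intercept is not identifiable for the primary outcome and should go; keeping it changes no estimate. The variance form is the part that matters. If no finite-sample correction is applied, the deciding interval is 3.9% to 4.4% too narrow and the type I error is about 6.0% to 6.1% for n = 220 to 199. If a residual-df, HC1 or HC2 variance is used, the level is about 5%. The treatment estimate is unaffected, and only results with a correct p of about 0.050 to 0.061 would change.

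This rests on all 15 sites entering the model, on approximately normal errors for the closed form, and on the simulation assumptions listed above. The redundancy and the plan's silence are certain from the text; actual inflation is not. No figure is claimed for the multiple-imputation branch.

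**What to change.** For the primary outcome, replace the mixed model with ANCOVA of the 48-week change in pct950 on treatment, baseline pct950 and site, without the participant random intercept. Fit it by least squares or REML with a residual-df variance, or with HC1 or HC2 if a robust variance is to be kept. Refer it to t on n − 17 df, where n is the number analysed. Stating degrees of freedom without fixing the variance form would not repair the level.

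For the multiple-imputation branch, use the same corrected variance within each of the 50 imputations, with small-sample pooled degrees of freedom based on a complete-data value of n − 17, n here being the size of each completed dataset. Keep the random-intercept model, with REML or a small-sample correction, for outcomes with repeated post-baseline values (spirometry and questionnaires).

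The cost is wording only; no visit, scan or sample size changes. The interval is 4.1% (n = 220) to 4.6% (n = 199) wider than the uncorrected one. Simulated power, uncorrected to corrected, at SD 4:

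| True difference | n = 220 | n = 199 |
|---|---|---|
| 2.0 | 96.3% to 95.6% | 94.5% to 93.5% |
| 1.5 | 80.8% to 78.6% | 76.8% to 74.1% |
| 1.0 | 48.1% to 45.0% | 44.6% to 41.2% |

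Power at the design effect stays above 90%. The power given up is power that the uncorrected test gains only by exceeding 5%.

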8.2. Secondary analyses

As indicated above, the same basic model specified above can be used for the secondary outcomes, most of which are continuous. For a binary secondary outcome, we will use the logistic regression analog in which $g()$ above is the logistic function, $g(u)=\log\{u/(1-u)\}$. Since the strict interpretation of odds ratios from mixed models with the logistic link is dependent on the value of the random effect variable (participant), we will also use maximum likelihood estimation and robust variance estimation described for the primary analysis above. The same assumptions and methods for missing data for the primary outcome will also be used in the secondary analyses.

In particular, we seek to estimate the treatment effect for each of 5 lobes of the lung. A simple approach is to use the basic change-from-baseline model described above separately for data from each lobe and then use a gate-keeper Chi-square test and Bonferroni correction to account for the multiplicity of tests. This method, while valid, does not provide evidence about the correlation among the estimates from the 5 lobes that is itself of scientific interest. Therefore, we will use a multivariate version of the GLMM from Section 8.1 that simultaneously estimates the treatment effect for the 5 lobes and produces both the 5 estimates of treatment effect as well as their covariance matrix³⁸. We will use these results to conduct gate-keeper Chi-square test of the null hypothesis that the 5 treatment effects are all the same across lobes and if this null is rejected, provide lobe-specific treatment effect estimates with 99% Bonferroni-corrected confidence limits to ensure that the joint coverage probability is 95%. In addition, we will also show estimates and 95% confidence limits for the between lobes correlations.

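### For continuous secondary outcomes measured repeatedly, a robust variance cannot correct the modest bias that a wrong random-intercept covariance causes when outcome-related dropout differs by arm

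*Combined protocol and SAP*

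**What the plan says.** Section 8.1 sets out one mixed model for all outcomes. Its only within-participant term "is a random intercept (to account for serial correlations in the within-patient responses"; no random slope, autoregressive or unstructured alternative is given. The mean model has time terms and, "if needed, interaction terms between the time covariates and the (trt) treatment group indicator". A robust variance "will be used to guard against incorrect inferences due to misspecification of the assumed serial correlation structure among repeated observations on each subject".

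Missing data are handled in the same section. The plan states: "We anticipate some degree of loss-to-follow-up (less than 10%) that will not affect our analyses". The model "will be estimated using the method of maximum likelihood so that missing data will effectively be imputed by their expected values given the other measurements". Then: "If the loss-to-follow is 10% or greater, then multiple imputation will be used to construct the 95% confidence limits", with 50 imputations. No imputation model is described.

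Section 8.2 reuses the model and the robust variance for the secondary outcomes and adds: "The same assumptions and methods for missing data for the primary outcome will also be used in the secondary analyses". By the schedule in section 4.1, SGRQ-C, mMRC, CAT and PROMIS-20a have four post-baseline visits (weeks 12, 24, 36, 48) and spirometry has two (weeks 24, 48). HRCT has one (week 48).

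**The concern.** The plan uses two protections for repeated outcomes: maximum likelihood for missing visits, and a robust variance for a wrong correlation structure. They are not independent. The value that maximum likelihood implicitly fills in for a missing visit is a prediction from that person's earlier visits, and the weights in that prediction come from the assumed covariance. A random intercept forces equal variance at every visit and equal correlation at every lag. In a trial about rates of progression, participants may well diverge over time, and then the weights are wrong. A robust variance changes the width of the confidence interval and leaves its centre where it was.

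At stake are the clinical secondary outcomes, by which the trial would show whether a CT effect carries over to lung function, symptoms and quality of life.

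**Working it through.** **Inputs from the protocol.** Visits as above (section 4.1); 110 per arm, which is 88/0.8 (section 8.5); 1:1 allocation (section 7.3). Section 8.5 gives an SD only for the primary outcome, so bias is expressed in SDs of the week-48 change. The plan gives no figure of its own on this point to reproduce.

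**Assumptions.** The true covariance, the dropout mechanism and the loss rates (8%, 15%, 20%) are assumed. Treatment-by-visit terms are taken to be in the model.

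**Step 1: the mechanism with two visits.** Let Y1 and Y2 be the baseline-adjusted changes at weeks 24 and 48, with Y1 seen in everyone and Y2 missing in some. Within an arm, maximum likelihood estimates the week-48 mean as

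mean(Y2, observed) + b × [mean(Y1, all) − mean(Y1, Y2 observed)],

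where b is the model's regression of Y2 on Y1. Let β be the true regression and D the bracketed term. If dropout depends only on Y1, the arm's bias is (b − β) × D, so

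bias of the contrast = (b − β) × (D_losartan − D_placebo).

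This is zero if the covariance is right (b = β), if dropout is completely random (both D are 0), or if the two D are equal, as they essentially are when both arms share one mechanism. No variance estimator enters the formula.

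Under a random intercept, b is the covariance divided by the average of the two variances, whereas β is the covariance divided by the week-24 variance. With V for variance, b/β = 2·V24/(V24 + V48). Equal variances give b = β. If participants diverge, V48 exceeds V24 and b is too small.

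**Step 2: simulated bias of the week-48 contrast** (400,000 participants per scenario, maximum likelihood, dropout driven by the last observed value). Opposite means that poor responders leave placebo and good responders leave losartan.

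| Fit, truth, dropout | 8% loss | 15% | 20% |
|---|---|---|---|
| Random intercept; random slopes, 4 visits, opposite | −0.04 | −0.07 | −0.10 |
| Random intercept; AR(1) 0.7, 4 visits, opposite | +0.02 | +0.03 | +0.04 |
| Random intercept; random slopes, 2 visits, opposite | −0.03 | −0.06 | −0.08 |
| Random intercept; random slopes, 2 visits, one arm only | −0.01 to −0.02 | −0.03 | −0.03 to −0.04 |
| Unstructured; every scenario | under 0.01 in size | under 0.01 | under 0.01 |

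With four visits, outcome-related dropout in one arm only also gave about half the bias of the opposite-direction case. The same mechanism in both arms gave about 0. With two visits and AR(1) 0.85 the random-intercept bias was below 0.005, as step 1 predicts for equal variances.

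**Step 3: formula against simulation.** A complete-case contrast has bias −β × (D_losartan − D_placebo), so random-intercept bias divided by complete-case bias should equal 1 − b/β at every loss rate. With two visits, random slopes and opposite dropout it was 0.035/0.110 = 0.32, 0.060/0.194 = 0.31 and 0.083/0.253 = 0.33. The ratio is stable. In this truth the planned model makes about 70% of the needed correction and leaves about 30%. Solving 2v/(1 + v) = 0.7 gives v = 0.7/1.3 = 0.54, so the assumed truth has a week-24 variance of roughly half the week-48 variance.

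**Step 4: size against the standard error.** With full data the SE is about √(2/110) = 0.135 SD; simulated robust SEs were 0.137 to 0.147, so take 0.14. With r = bias/SE, two-sided type I error ≈ Φ(−1.96 − r) + 1 − Φ(1.96 − r).

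| Bias (SD) | r | Type I error |
|---|---|---|
| 0.02 | 0.14 | 5.2% |
| 0.04 | 0.29 | 5.9% |
| 0.07 | 0.50 | 7.9% |
| 0.10 | 0.71 | 11.0% |

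These are normal approximations. A finite-sample check (220 participants, 600 runs) covered a correct random intercept (bias at most 0.009, Monte Carlo SE 0.006, coverage 93% to 96%) and AR(1) 0.7 with random dropout (bias −0.001 and −0.007, coverage 95%). It did not reach the opposite-direction cases under a wrong covariance.

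**Step 5: 10% loss or more.** The 15% and 20% columns describe maximum likelihood, which the plan then replaces by multiple imputation. Imputing from the same random-intercept model uses the same b, so step 1 gives the same bias. An imputation model that estimates b freely removes it.

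**Step 6: precision.** In a separate simulation with an assumed week-48 SD of 16 points and 11–15% missing, the two fits had SEs of 2.27 and 2.26 points, a difference of 0.4%. Its random-intercept bias under opposite dropout was 1.4 points, or 1.4/16 = 0.09 SD, which is of the same order as above.

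**The case against.** The case against is substantial. Where the plan relies on maximum likelihood alone (below 10% loss), the worst scenario tried shifts the contrast by 0.3 SE. That scenario has dropout running in opposite directions by arm, which nothing in the documents predicts. Sections 7.5 and 7.6 keep participants in follow-up after treatment stops, which limits loss. Section 8.3 estimates the autocorrelation matrix by treatment group before the main analyses, so the correlation structure will be looked at. Section 8.2 offers the basic model for secondary outcomes without making it rigid. All of this stands and limits the size. It does not remove the point: section 8.3 attaches no decision to the autocorrelation matrix, and no other covariance is named.

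A reader might infer that any dropout biases these estimates. It does not: the covariance must be wrong and outcome-related dropout must differ by arm. A reader might also infer that the plan claims its robust variance cures dropout bias. Section 8.1 does not say so; it gives the robust variance its usual role and treats missing data separately. Finally, the error rates at 15–20% loss should not be read as the plan's own, because multiple imputation applies there. Since its model is unstated, protection in that range is uncertain rather than absent.

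**Conclusion.** The point holds in a limited form. For continuous secondary outcomes with repeated follow-up, the only stated guard against a wrong random intercept acts on the standard error and cannot re-centre the week-48 contrast. Under assumed random slopes and opposite-direction dropout the bias is about 0.04 SD at 8% loss (0.3 SE, type I error about 6%), and about half that if only one arm has outcome-related dropout. At 15–20% loss it would be 0.07 to 0.10 SD (0.5 to 0.7 SE) if the analysis, or the imputation model, kept the random-intercept structure.

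These sizes rest on assumed covariance and dropout models. The documents do not show what bias, if any, this trial would have, or in which direction. It would be wrong to extend the point to the primary outcome, which has a single follow-up scan and so no serial correlation to misspecify. This is a cheap improvement to the secondary analyses and no threat to the main conclusion.

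**What to change.** In sections 8.1 and 8.2, for continuous outcomes with more than one post-baseline visit:

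- replace the random intercept by an unstructured within-participant covariance;
- use categorical visit and treatment-by-visit terms as standard, rather than only when needed, and name the week-48 contrast as the estimate;
- keep the robust variance for standard errors;
- state the imputation model for the 10% rule: impute by arm, using all earlier visits, with an unstructured covariance.

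Leave the logistic models for binary outcomes outside this change.

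The cost is SAP wording and a few more variance parameters: 4 × 5/2 = 10 for four visits and 2 × 3/2 = 3 for two, which is small for 220 participants. The loss of precision is negligible (step 6 of the working).
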